### **Safety Analysis Set (SAF)**

SAF includes all patients who have completed the core study and have received at least one dose of study medication in the extension study. Patients will be analyzed according to the

treatment received during the core study. Patients will be analyzed as receiving zoledronic acid in core study if they received at least one dose of zoledronic acid in core study.

All safety analyses will be performed using SAF.

### **Pooling of centers**

Centers will be pooled into four regions based on the similarity of clinical practice for randomization and analysis purpose. The regions are as follows:

- North America region
  - United States
  - Canada
- EMEA America region
  - Belgium
  - Finland
  - Germany
  - Hungary
  - Italy
  - Poland
  - Romania
  - Russia
  - South Africa
  - Sweden
  - Turkey
  - United Kingdom
- Latin America region
  - Brazil
- APAC region
  - Australia
  - New Zealand

### **Patient disposition**

The number and percentage of patients in the following categories will be tabulated and listed by core treatment group within the FAS:

- Completed extension study
- Discontinued extension study

Discontinuations will be further broken down by reason.

In addition, recruitment will be summarized by country and then center.

A complete listing of patient disposition will be provided for FAS.

Demographic information and reasons for discontinuing will be provided in a listing for screen failure patients.

### **Protocol deviations**

Protocol deviations will be summarized in a table and will be listed for all FAS patients by core treatment group. The number of patients with any protocol deviation will also be summarized.

### **Patients in each analysis set**

The number and percentage of patients in each analysis set (FAS, SAF) will be summarized by core treatment group. Listing of these analysis sets will be provided as well.

### **Demographic and other baseline characteristics**

[figure not shown]
Demographic variables and baseline characteristics will be summarized at both core and extension baselines.

Baseline demographic information for continuing patients was collected at the beginning of the Core study and will not be collected again in the extension study.

Descriptive statistics for the following demographic variables and baseline characteristics will be summarized for core period by core treatment group using FAS. Similar summaries will be performed for extension period but sex, race, ethnicity and non-vertebral fractures will be excluded. Vertebral morphometry will be removed as well because it is no longer an endpoint in the extension period.

Age at extension enrollment (years)

- Age group at extension enrollment ( $\geq 6$  years to  $\leq 9$  years;  $\geq 10$  years to  $\leq 19$  years)
- Sex
- Race
- Ethnicity

- 
- Weight (kg)
  - BMI ( $\text{kg}/\text{m}^2$ ). The baseline standing height will be used in BMI calculation.
  - Tanner evaluation (breast development, genital stage, pubic hair, and whether menarche has occurred)
  - Lumbar spine BMD Z-score
  - Lumbar spine BMD Z-score category
    - $\leq -2.0$
    - $> -2.0$  to  $\leq -1.0$

- $> -1.0$  to  $\leq -0.5$
- Lumbar spine Bone Mineral Content (BMC) (g)
- Total body BMC (g)
- Serum 25-hydroxy vitamin D (nmol/L)
- Serum calcium level (mmol/L)
- Serum NTX (nmol BCE/L)
- Serum TRAP-5b (U/L)
- Serum BSAP (ng/mL)
- Serum P1NP (ng/mL)
- Vertebral morphometry
- Non-vertebral fractures
- Metacarpal cortical width (mm)

- Pain score

In addition, the core baseline comparability between core treatment groups will be evaluated for demographic and other baseline characteristics variables. Categorical variables will be evaluated using Fisher's exact test, and the continuous variables will be evaluated using a Wilcoxon rank-sum test.

Note that these tests of comparability are performed for descriptive purpose only, and will not be considered to define any formal basis for determining factors which should be included in statistical analysis models. However, when these tests yield significant results they can be used as extra information in interpreting any treatment-by-factor interactions that are observed in the sensitivity analyses performed on the primary and secondary efficacy variables.

All demographic and baseline characteristic data will be listed as presented above.

### **Disease-related background information**

Disease-related background and historical information will be summarized by type of disease (Duchenne muscular dystrophy, rheumatic condition or inflammatory bowel disease) and by type (as specified in the CRF) within rheumatic condition and inflammatory bowel disease. Counts and percentages will be provided by core treatment group.

- Rheumatic conditions:
  - Systemic onset Juvenile Idiopathic Arthritis (JIA)
  - Polyarticular rheumatoid factor positive JIA
  - Polyarticular rheumatoid factor negative JIA
  - Psoriatic arthritis JIA
  - Enthesitis-related arthritis JIA

- Oligoarticular arthritis JIA
- Unclassified JIA
- Systemic lupus erythematosus (SLE)
- Juvenile dermatomyositis
- Scleroderma (generalized or localized)
- Overlap syndromes (including mixed connective tissue disease)
- Sjogren's syndrome
- Giant cell (temporal) arteritis
- Takayasu's arteritis
- Polyarteritis nodosa
- Wegener's granulomatosis
- Churg-Strauss syndrome
- Microscopic polyangiitis
- Essential cryoglobulinemic vasculitis
- Cutaneous leukocytoclastic angiitis
- Behcet's disease
- Other vasculitis
- Inflammatory bowel disease:
  - Crohn's disease
  - Ulcerative colitis
- Duchenne muscular dystrophy
- Others

Frequency counts will be provided by core treatment group as well as the total in a table. A listing will also be generated.

### **Relevant medical history and current medical conditions**

The relevant medical history/current medical conditions for the extension study include relevant medical history/current medical conditions recorded in Core study and adverse events occurring during the Core study or after the end of Core study but before the first study drug infusion in the extension study. The number and percentage of patients with relevant medical history/current medical conditions for the extension study will be presented for each core treatment by primary system organ class and preferred term of the MedDRA dictionary. A patient with multiple occurrences of a medical condition/adverse event for a preferred term or system organ class is counted only once in each specific category. A corresponding listing will also be provided.

All analyses will be performed separately based on the FAS.

### **Extent of exposure**

A summary table will be provided for the exposure to study medication, including number of patients with any infusion, duration for 1st infusion, duration for 2nd infusion, volume for 1st infusion, and volume for 2nd infusion.

## **Prior/concomitant medications and significant non-drug therapies**

The number and percentage of patients receiving prior and concomitant medications and significant non-drug therapies will be summarized by core treatment group and preferred term according to the WHO Drug Reference List employing the Anatomical Therapeutic Chemical (ATC) classification system. Prior medications are defined as those ending prior to the first infusion of study drug in the extension study; medications ending on or after the first infusion of study drug in the extension study are concomitant medications. Prior medications will be presented separately from concomitant medications. The summary table will first be sorted by ATC class alphabetically and then by preferred term in decreasing order of frequency with respect to usage in the zoledronic acid group.

Furthermore, summarizations by ATC class will be provided with regard to a group of specified concomitant medications/significant non-drug therapies, which include osteoporosis-related medications, nutritional supplements, and glucocorticoids. The summary table will be sorted by ATC class in decreasing order of frequency in the zoledronic acid group.

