9.3 Treatments

Study drug and compliance

Descriptive statistics will be provided by core treatment group for duration of infusion and volume of infusion.

Concomitant therapy

Concomitant medications will be coded using the WHO Drug Reference List that employs the Anatomical Therapeutic Chemical (ATC) classification system. Summary tables will be provided that present the number and percent of patients receiving those medications by preferred term and treatment for medications prior to the first dose in the extension and during the 12-month extension period. The medications will be sorted in decreasing order of frequency with respect to usage in the zoledronic acid group.

Descriptive statistics will be provided by core treatment group for the dose and duration of use of GCs prior to the first dose in the extension and during the 12-month extension period for Group 1. The number and percentage of patients receiving different types of GC therapy will be presented by preferred term and Core treatment group (zoledronic acid or placebo).

Similar summary tables will be provided that present the number and percent of patients receiving those medications by preferred term and treatment for medications prior to the first dose in the extension and during the 12-month extension period for Group 2.

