## **Missing date convention**

If the medication start and end dates are recorded in the CRFs, medications that start on or prior to the first infusion in the extension study and end on or after the first infusion in the extension study including ongoing at end of the extension study were included in both prior to and after start of study drug administration in the study, respectively.

Partial medication start dates will be imputed as follows:

- Only day is missing: the partial start date will be imputed using 15MONYYYY if the month and year indicate that the medication started prior to the first infusion of extension study medication or 01MONYYYY if the month and year indicate that the medication started on or after the first infusion of extension study medication.
- Both day and month are missing: the partial start date will be imputed using 01JULYYYY if the year indicates that the medication started prior to the first infusion of extension study medication or max(01JANYYYY, treatment start date+1) if the year indicates that the medication started on or after the first infusion of extension study medication.

Partial medication end dates will be imputed as follows:

- Only day is missing: the partial end date will be imputed using the last date of the month.
- Both day and month are missing: the partial end date will be imputed as December 31 if the end year is prior to the year of first infusion of extension study medication or one day after the last extension study infusion date if end year is equal to or after the year of first infusion of extension study medication.

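### The SAP gives two conflicting rules for medications that span the first extension infusion, so the prior-medication table by core arm is not determined; its partial-date rules can also give impossible dates

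*SAP*

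**What the plan says.** **End-date rule** (SAP, Prior/concomitant medications and significant non-drug therapies). A drug is prior only if it had stopped before that infusion; by contrast, "medications ending on or after the first infusion of study drug in the extension study are concomitant medications". The classes are therefore mutually exclusive, and "Prior medications will be presented separately from concomitant medications", by core treatment group. A further summary of osteoporosis drugs, nutritional supplements and glucocorticoids covers concomitant use only.

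**Both-periods rule** (SAP, Missing date convention for medications). Where start and end dates are recorded, "medications that start on or prior to the first infusion in the extension study and end on or after the first infusion", including those still ongoing at the end of the study, "were included in both prior to and after start of study drug administration in the study, respectively".

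**Protocol 9.3** asks for patients receiving "medications prior to the first dose in the extension and during the 12-month extension period", and for glucocorticoid dose and duration over the same two periods in Group 1.

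**Partial dates** (same SAP convention).
- Year-only end: 31 December if the year precedes the first-infusion year, otherwise "one day after the last extension study infusion date if end year is equal to or after the year of first infusion".
- Year-only start: "01JULYYYY if the year indicates that the medication started prior to the first infusion of extension study medication"; if on or after it, the later of 1 January and treatment start + 1.
- Start with only the day missing: the 15th if before the first infusion, the 1st of the month if on or after it.

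The SAP's adverse-event convention sets a start in the infusion month and year to the later of the 1st and treatment start + 1. It also resets an imputed start to a complete end date when the start falls after it. The medication convention has neither the reset nor, for a missing day, the floor.

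**The concern.** Two programmers following this SAP could produce different prior-medication tables by core arm. The drugs affected are those already in use at Visit 9. Glucocorticoid treatment defines the population. Protocol 5.1.2 requires adequate calcium and vitamin D intake from Visit 8/8A to the final visit, by diet, supplement or both, so recorded supplements will often span Visit 9. Under the end-date rule the prior table shows only drugs that had been stopped, which is not the pre-extension use that Protocol 9.3 asks for. The concomitant-only glucocorticoid and supplement summary does not replace it, because it does not separate continuing users from new starters.

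The date rules are a separate defect. They can give dates that contradict the recorded year or a known start or end, and so would corrupt any duration computed from them.

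**Working it through.** The documents give no figure to reproduce. The check applies the SAP rules to example records; all calendar dates below are assumptions.

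**1. Classification** (first infusion 15 Sep 2016)

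| Record | End-date rule | Both-periods rule |
|---|---|---|
| Ended 1 Aug 2016 | prior | prior |
| 1 Jan to 1 Dec 2016 | concomitant | both |
| Glucocorticoid from 1 Jan 2015, ongoing | concomitant | both |
| Calcium/vitamin D from 20 Aug 2016, ongoing | concomitant | both |
| Started on the infusion day, ended 20 Sep 2016 | concomitant | both |
| 1 Oct to 1 Nov 2016 | concomitant | concomitant |

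The rules differ for every spanning record and for no other. The concomitant column is the same under both.

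**2. Size in the prior table.** Let c be the share of children with a record that ended before the infusion, and s the share with a spanning record only.
- End-date rule: c. Both-periods rule: c + s. Gap: s.
- Illustration: c = 20%, s = 70% gives 20% against 20% + 70% = 90%.
- Range: with c held at 20%, s can run from 0 to 80%, so the second figure runs from 20% to 100% while the first stays at 20%.

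**3. Year-only end dates**
- Infusions 10 Oct 2016 and 10 Apr 2017, end recorded as 2016: imputed 11 Apr 2017, which is 31 + 28 + 31 + 11 = 101 days after that year closed.
- Infusions 10 Feb and 10 Aug 2016, end recorded as 2017: imputed 11 Aug 2016, which is 20 + 30 + 31 + 30 + 31 + 1 = 143 days before that year began.
- Infusions 15 Mar and 15 Sep 2016, known start 10 Nov 2016, end recorded as 2016: imputed 16 Sep 2016, before the start.

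Frequency, given a year-only end: take the first infusion at fraction f of the year, uniform on (0, 1), the second at f + 0.5 (the protocol's 6-month interval), and the true end uniform over the 12 months after f.
- For f < 0.5 the imputed year is the first-infusion year, which is wrong with probability f. Integrated over 0 to 0.5, this is 1/8.
- For f > 0.5 the imputed year is the next one, which is wrong with probability 1 − f. Integrated over 0.5 to 1, this is 1/8.
- Total 1/4, or 25%.

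Effect on classification: none. The imputed date always follows the first infusion, so the drug is concomitant. 31 December of the recorded year, capped at last contact, is also on or after the first infusion.

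**4. Partial start dates**
- Infusion 10 Oct 2016, supplement begun later that month, day missing. If the month is treated as on or after the infusion, the start becomes 1 Oct 2016, which is 10 − 1 = 9 days too early. Under the both-periods rule the drug then enters the prior table. Under the end-date rule start dates play no part, so nothing changes.
- Start recorded as 2015, known end 20 Mar 2015: imputed start 1 Jul 2015, after the end.

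**The case against.** The best defence is that little depends on this. Medications ending on or after the first extension infusion are concomitant under either rule, so the concomitant table and the glucocorticoid and supplement summary are identical. The tables are descriptive, and no SAP model uses the classification. That stands. A reader might infer that continuing drugs vanish, or that the background therapy needed to read the bone and calcium safety results depends on which sentence is programmed. The documents do not support either inference: during-extension therapy is unchanged, and only the description of pre-extension use is at stake.

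It can also be said that the both-periods sentence sits under a missing-date heading. But it applies where dates are recorded, so it is a classification rule, and the SAP does not say which rule governs.

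Three limits on the date rules also stand.
- The year-only end rule moves no drug between tables, and the SAP itself plans no medication-duration summary. The distortion arises only if the glucocorticoid duration in Protocol 9.3 is produced.
- The early start needs a particular reading, because month and year alone do not show that a drug begun in the infusion month began after the infusion.
- Protocol 6.3 promises dose and intake dates only for osteoporosis drugs, supplements and glucocorticoids, so these rules matter chiefly there.

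Nor can one assume that nearly every child would have a prior supplement record, since Protocol 5.5.3.2 allows intake by diet alone.

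**Conclusion.** The conflict is real and affects every medication that spans the first extension infusion. It leaves the prior-medication table by core arm undetermined, and the end-date rule does not deliver the pre-extension use requested in Protocol 9.3. The gap equals the share of children whose only qualifying record spans the infusion. The 20% against 90% contrast rests on an assumed mix; the direction does not.

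The partial-date faults are separate and do not cause the omission from the prior table. Year-only ends would fall outside their recorded year in about 25% of such records under the uniform assumptions, with no effect on prior or concomitant counts. The start-date fault affects the prior table only under the both-periods rule and the on-or-after reading. How often dates are partial is not stated. No primary or efficacy analysis changes. This should be corrected before programming, but it does not threaten the trial's conclusions.

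**What to change.** In the SAP:

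1. Define prior as started before the first extension infusion, whatever the end date, and concomitant as ended on or after it or ongoing. Count spanning drugs in both tables. Starting strictly before keeps a drug begun on the infusion day out of the prior table.
2. Impute a year-only end in or after the first-infusion year as 31 December of the recorded year, capped at the last contact date and never before the start.
3. For a missing start day in the infusion month, use max(01MONYYYY, first extension infusion + 1), unless a known end date is before the infusion. In that case apply the existing pre-infusion rule.
4. Add the check already used for adverse events: an imputed start that falls after the end is reset to the end date.

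The exception in item 3 and the check in item 4 are both needed. Take an infusion on 10 Oct 2016, a start of October 2016 and a known end of 5 Oct 2016. The maximum alone gives a start of 11 Oct, so the drug would be neither prior nor concomitant and would drop out of both tables. With items 3 and 4 the start becomes 15 Oct, is reset to 5 Oct, and the drug is correctly prior. Item 4 also repairs the 2015 example.

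The cost is a few sentences of SAP text and minor programming, with no new data.

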## **Missing date convention**

If the medication start and end dates are recorded in the CRFs, medications that start on or prior to the first infusion in the extension study and end on or after the first infusion in the extension study including ongoing at end of the extension study were included in both prior to and after start of study drug administration in the study, respectively.

Partial medication start dates will be imputed as follows:

- Only day is missing: the partial start date will be imputed using 15MONYYYY if the month and year indicate that the medication started prior to the first infusion of extension study medication or 01MONYYYY if the month and year indicate that the medication started on or after the first infusion of extension study medication.
- Both day and month are missing: the partial start date will be imputed using 01JULYYYY if the year indicates that the medication started prior to the first infusion of extension study medication or max(01JANYYYY, treatment start date+1) if the year indicates that the medication started on or after the first infusion of extension study medication.

Partial medication end dates will be imputed as follows:

- Only day is missing: the partial end date will be imputed using the last date of the month.
- Both day and month are missing: the partial end date will be imputed as December 31 if the end year is prior to the year of first infusion of extension study medication or one day after the last extension study infusion date if end year is equal to or after the year of first infusion of extension study medication.

## Efficacy evaluation

Analyses of all efficacy endpoints will be performed on FAS. All relevant efficacy measurements will be presented in listings. Core study measurements will be listed as well for analyses that require both core and extension study measurements.

## Analysis for efficacy variables

If otherwise not specified, the efficacy data will be summarized and analyzed with respect to core baseline only and will be presented by the core treatment group and visit. The mean, median, standard deviations, and range of each variable and its change from baseline measured on a continuous scale, will be presented by core treatment group and visit. Number and percentage of patients will be presented for categorical variables by core treatment group and visit. All hypothesis tests will be evaluated at a 0.05 level of significance, and the p-values will be rounded to the 4th decimal place. Change from baseline at Month X is defined as value at Month X - value at baseline. Percentage change from baseline is defined as 100 times the change from baseline divided by the baseline value. Missing values will not be imputed or replaced.

The efficacy variables and their analysis methods are described below.

- **Percent change in lumbar spine areal BMD Z-score at Months 18 and 24 relative to baseline, zoledronic acid group vs. placebo**

The percent change in LS-BMD Z-score at Months 18 and 24 relative to core baseline between zoledronic acid and placebo (the core treatment groups) will be evaluated using an ANCOVA model with core treatment, pooled center, underlying condition treated with glucocorticoids and core baseline LS-BMD Z-score as explanatory variables and pooled centers as random effect.

From the model, core treatment difference in least squares means between zoledronic acid group vs. placebo group will be estimated and presented together with two-sided 95% CI and p-value. In the same table, the LS means and standard errors for percent change from baseline in LS-BMD Z-score at Month 18 and Month 24 will be presented for each core treatment group. Descriptive statistics will also be shown for baseline, Month 18 and Month 24 visits.

- **Change in lumbar spine and total body BMC at Months 18 and 24 relative to baseline, zoledronic acid group vs. placebo**

The change in BMC at the lumbar spine and total body at Months 18 and 24 relative to core baseline between zoledronic acid and placebo will be evaluated using an ANCOVA model with core treatment, pooled center, underlying condition treated with glucocorticoids and core baseline BMC as explanatory variables and pooled centers as random effect.

From the model, core treatment difference in least squares means between zoledronic acid group vs. placebo group will be estimated and presented together with two-sided 95% CI and p-value. In the same table, the LS means and standard errors for change from baseline in lumbar spine or total body BMC at Month 18 and Month 24 will be presented for each core treatment group. Descriptive statistics will also be shown for baseline, Month 18 and Month 24 visits.

- **Relative change in biochemical markers of bone turnover (Serum NTX, TRAP-5b, BSAP and P1NP) at Months 18 and 24 relative to baseline, zoledronic acid group vs. placebo**

The analysis of changes from core baseline to Month 18 and Month 24 in the biochemical markers, serum NTX, TRAP-5b, BSAP, and P1NP will be performed as follows: a transformation of the  $\log_e$  ratio of post-baseline value vs. baseline value at each visit will be used to normalize the distribution of the biochemical marker parameters. An ANCOVA model with core treatment group, pooled centers, underlying condition treated with glucocorticoids, and  $\log_e$  (core baseline value) as explanatory variables and pooled centers as random effect will be used on the transformed data at each post-baseline time point.

From the model, core treatment difference in least squares means between zoledronic acid group vs. placebo group in log scale will be estimated and presented together with two-sided 95% CI and p-value. Estimated core treatment difference and two-sided 95% CI will then be transformed back to the original scale and displayed on the table. In the same table, the LS means and standard errors in both log scale and original scale for change from baseline for the biomarkers at Month 18 and Month 24 will be presented for each core treatment group. Descriptive statistics will also be shown for baseline, Month 18 and Month 24 visits in both original scale and log scale. A plot will be generated for each biochemical marker over core and extension study period respectively.

- **Incidence of new vertebral fractures and new morphometric vertebral fractures during the 12 month extension period, zoledronic acid group vs. placebo**

The number and percentage of patients with new vertebral fractures and new morphometric vertebral fractures during the 12 month extension period will be presented by core treatment group. Between-treatment differences will be evaluated using Fisher's exact test. New vertebral fractures are defined as fractures of Genant grade 1 or higher that occur at lumbar or thoracic spine from first extension dose infusion to the end of the extension study. New morphometric vertebral fractures during the 12 month extension period is defined as a morphometric vertebral fracture present at Month 24 X-ray which is not present at extension baseline.

- **Change in 2nd metacarpal cortical width at Month 24 relative to baseline, zoledronic acid group vs. placebo**

The change in 2nd metacarpal cortical width at Month 24 relative to core baseline will be evaluated using an ANCOVA model with core treatment, pooled center, underlying condition treated with glucocorticoids and core baseline bone age as explanatory variables and pooled centers as random effect.

From the model, core treatment difference in least squares means between zoledronic acid group vs. placebo group will be estimated and presented together with two-sided 95% CI and p-value. In the same table, the LS means and standard errors for change from baseline in 2nd metacarpal cortical width at Month 24 will be presented for each core treatment group. Descriptive statistics will also be shown for baseline and Month 24 visits.

[figure not shown]
Above analysis will be carried out with respect to both baselines (core baseline as well as extension baseline).

[figure not shown]
- **Reduction in pain from baseline, zoledronic acid group vs. placebo**

[figure not shown]
Pain is assessed using Faces Pain Scale-Revised (FPS-R) at first infusion in the extension study (Visit 9), Month 15, 18, 21 and 24, which ranges from 0 (No Pain) to 10 (Very Much Pain). Details of FPS-R can be found in Appendix section “Faces Pain Scale” in the protocol.

The reduction in pain from core baseline by visit will be evaluated based on whether or not patients have a decrease in their FPS-R from baseline. If pain remains the same or worsens from baseline a patient will be classified as ‘0’ and if the pain scale decreased then the patient will be classified as ‘1’. Whether or not a patient experiences a decrease in pain will be evaluated using a logistic regression model with core treatment, pooled centers, underlying condition treated with glucocorticoids and baseline pain score as explanatory variables.

Regression analysis will be carried out with respect to both baselines (core baseline as well as extension baseline).

[figure not shown]

